6/14/2021

Pleural Manometry for the Characterization of
Spontaneous and Tension Pneumothorax

NCT04630301

Date: 06/14/2021

Principal Investigator: [name]

Application Number: IRB00256185

JHM IRB - eForm A – Protocol

- **Use the section headings to write the JHM IRB eForm A, inserting the appropriate material in each. If a section is not applicable, leave heading in and insert N/A.**
- **When submitting JHM IRB eForm A (new or revised), enter the date submitted to the field at the top of JHM IRB eForm A.**

1. Abstract

A pneumothorax is defined as the presence of air within the pleural space. Patients can be asymptomatic, have mild dyspnea, or significant chest pain and dyspnea, and even hemodynamic instability in the case of a tension pneumothorax (TP).¹ The historical teaching for the cause of hemodynamic instability has been increased pressures within the pleural space causing a shift of the mediastinum, “kinking” of the inferior vena cava and a reduction in cardiac output. Expert guidelines define TP as when the intrapleural pressure (Ppl) is greater than atmospheric pressure for much of the respiratory cycle.² Therefore, it follows that Ppl in patients without tension remains below atmospheric pressure for much of the respiratory cycle. However, these manometric definitions remain controversial as Ppl in TP has never been measured and data on Ppl on hemodynamically stable patients is limited. There remains a gap in our current understanding of the pathophysiology of these disease processes. Exploring this unknown can be of clinical significance as pleural manometry is being employed in patients with pleural effusions to guide management. By using recently demonstrated pleural manometric techniques, this study aims to characterize the intrapleural pressures in patients with pneumothorax.

2. Objectives

Primary objectives:

1. Describe the intrapleural pressure throughout the respiratory cycle in patients with pneumothorax.

Secondary objectives:

1. Demonstrate a relationship between initial intrapleural pressure and presence of persistent air leaks, need for prolonged chest tube drainages, pleurodesis, intrabronchial valve (IBV) placement, and/or video-assisted thorascopic surgery (VATS).

3. Background

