The rate of hospitalization for spontaneous pneumothorax among people age 14 or older is approximately 227 per million.³ Spontaneous pneumothorax in the absence of trauma can be further classified as primary spontaneous pneumothorax (PSP) or secondary spontaneous pneumothorax (SSP) based on the absence or presence of underlying structural lung disease, respectively. Though recent studies suggest that in some cases conservative management with close observation is an acceptable treatment, definitive evacuation remains a cornerstone of management for patients who are symptomatic or who have a large pneumothorax.⁴ Intrapleural

Date: 06/14/2021

Principal Investigator: [name]

Application Number: IRB00256185

air can be removed by either needle aspiration or introduction of a watersealed catheter into the pleural space. In the event of TP, emergent chest thoracostomy is preferred. In all cases, the goal of treatment remains to re-expand the affected lung, after which the catheter may be removed. If the visceral pleural defect is not healed after 5 days, it is deemed a persistent air leak. In these cases, the chest tube is maintained and more aggressive measures such as pleurodesis, placement of an IBV, or VATS are performed. Unfortunately, there is currently no method to predict which patients will require these more invasive procedures.

The lack of prognostic indicators is not the case in pleural effusions, however. Pleural manometry has been shown to be a useful tool in the management of patients with effusions. Doelken et al. described using an overdamped water manometer or an electronic transducer connected to a thoracentesis catheter for the direct measurement of Ppl with similar accuracy.⁵ Traditionally, thoracenteses are aborted after onset of dyspnea or cough, all fluid is drained, or 1L of fluid has been removed. This 1L limit exists to avoid the feared complication of reexpansion pulmonary edema. However, monitoring of Ppl during drainage and aborting the procedure once Ppl drops below -20 cmH₂O allows for safe drainage of often larger volumes.⁶⁻⁷ Furthermore, Lan et al. demonstrated that Ppl could diagnose non-expandable lung and predict pleurodesis failure in patients with malignant effusion.⁸ Lee et al, recently reported the use of a simple, in-line, digital manometer to measure Ppl in patients with pleural effusion.⁹

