Criteria for recruitment into this study include patients aged 18 or older admitted with clinical or radiographic evidence of new pneumothorax who are referred to Interventional Pulmonology for needle aspiration or tube thoracostomy. TP will be defined as a pneumothorax that results in mean arterial pressure <65 or systolic BP < 90.

Exclusion criteria include bilateral pneumothorax and pregnancy.

6. Drugs/ Substances/ Devices

No medical drugs, substances, or devices are being studied.

7. Study Statistics

- a. Primary outcome variables: Inspiratory Ppl, Expiratory Ppl, and Mean Ppl.
- b. Secondary outcome variables: Duration of chest tube placement, referral for pleurodesis, IBV placement, and/or referral for VATS.

Date: 06/14/2021

Principal Investigator: [name]

Application Number: IRB00256185

- c. Statistical plan: A student's t-test will be used to determine statistical significance in differences of Ppl between SP and TP. A student's t-test will be used to determine statistical significance in differences of Ppl in the secondary outcomes listed above. A sample size of 100 SP and 25 TP will be used based on expected incidence of disease in recruitment period. Enrollment will be competitive across all sites and the Coordinating Center (JHU's IP research team) will immediately alert PIs and Study Coordinators at the other sites if enrollment is paused or completed.
- d. Early stopping rules: Consistent inability to measure Ppl in TP. If study is stopped early, all sites will immediately be notified by JHU's IP research team to terminate enrollment.

8. Risks

- a. Enrolled patients will be only those already planned to receive chest tubes or needle aspiration; therefore, this study poses the same risks as these standard procedures. These risks include bleeding, infection, and local tissue damage. The study may delay evacuation of pneumothorax up to 30 seconds while Ppl are being recorded. These risks are independent of participation or non-participation in our study. No provisions are made for a research study-specific injury to the subject.
- b. Risks will be mitigated by using the same standard of care for chest tube or needle aspiration. Overall, the delay in chest tube placements will be minimized and negligible by limiting measurement time to 30 seconds.

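### Section 7c plans a two-group t-test for chest-tube duration, a time with no stated cut-off, and no direct test of persistent air leak, the first item of the secondary objective

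*Combined protocol and SAP*

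**What the plan says.** The secondary objective in section 2 is to "Demonstrate a relationship between initial intrapleural pressure and presence of persistent air leaks, need for prolonged chest tube drainages, pleurodesis", and it goes on to IBV placement and VATS. Section 3 defines the first item: "If the visceral pleural defect is not healed after 5 days, it is deemed a persistent air leak". It then adds: "In these cases, the chest tube is maintained and more aggressive measures such as pleurodesis, placement of an IBV, or VATS are performed".

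Section 7b lists the secondary outcome variables as "Duration of chest tube placement, referral for pleurodesis, IBV placement, and/or referral for VATS". Section 7c gives one method for all of them: "A student's t-test will be used to determine statistical significance in differences of Ppl in the secondary outcomes listed above". The Ppl measure could be any of three, since 7a reads "Primary outcome variables: Inspiratory Ppl, Expiratory Ppl, and Mean Ppl".

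For numbers, 7c says only "A sample size of 100 SP and 25 TP will be used based on expected incidence of disease in recruitment period". It states no alpha, power, effect size or SD.

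**The concern.** The method and the variable list do not fit the objective in two places.

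- **Duration.** A Student's t-test compares mean Ppl between two groups. Pleurodesis, IBV and VATS each give a yes/no grouping. Duration does not, unless it is cut. The objective speaks of prolonged drainage and section 3 cites a study that compared Ppl by prolonged drainage, but neither gives a threshold. The study is nonblinded (4g), and nothing in the plan stops the threshold being chosen once Ppl and duration are both known.
- **Persistent air leak.** It leads the objective and has a definition, but it is missing from 7b, so the 7c test does not reach it. It is also not named in the outcome data of 4a, although that list is open-ended.

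At stake is the secondary objective: one listed outcome has a test that is not fully specified, and one stated aim has no test of its own.

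**Working it through.** **Step 1: match objective, variables and test.**

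| Item in section 2 | In 7b? | Two groups for a t-test? |
|---|---|---|
| Persistent air leak | No | Yes, by the section 3 definition, but no test is planned |
| Prolonged drainage | As duration, a time | No; no cut-off is given |
| Pleurodesis | Yes (referral) | Yes |
| IBV | Yes | Yes |
| VATS | Yes (referral) | Yes |

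The conclusion rests on this table. The sample size cannot be reproduced, because 7c bases it on expected incidence and gives no inputs for a power calculation.

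**Step 2: how much the cut-off matters (illustration).** All inputs are assumed, apart from n = 100 + 25 = 125 from 7c. They are: every patient has a tube, two-sided alpha 0.05, Ppl–duration correlation ρ = 0.25 on the log scale, log-normal duration with median 4 days and log-SD 0.8, no Ppl or duration shift between SP and TP, and no duration altered by a procedure.

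For a split at *k* days, c = ln(k/4)/0.8, the share above is q = 1 − Φ(c), and the efficiency relative to the uncut variable is E = φ(c)²/[q(1 − q)]. Power ≈ Φ(atanh(ρ√E)·√122 − 1.96).

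- 5 days: c = 0.279, q = 0.390, E = 0.3837²/(0.390 × 0.610) = 0.619. ρ√E = 0.197, and 0.1993 × 11.05 = 2.20, so power ≈ Φ(0.24) = 60%.
- 10 days: c = 1.145, q = 0.126, E = 0.2070²/(0.126 × 0.874) = 0.389. ρ√E = 0.156, and 0.1572 × 11.05 = 1.74, so power ≈ Φ(−0.22) = 41%.
- Spearman: expected rank correlation (6/π)·arcsin(0.25/2) = 0.239, and 0.2441 × 11.05 = 2.70, so power ≈ Φ(0.74) = 77%.

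Simulation agrees with all three to within about a percentage point.

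**Step 3: range.** These simulated figures are for tests adjusted for SP/TP status, which differ little from unadjusted ones when there is no shift.

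- With ρ = 0.20 or 0.30, Spearman has 56% or 90% power and the 5-day split 41% or 76%.
- With medians of 3–6 days and log-SD of 0.6–1.0, the 5-day split gives 50–61% and the 10-day split 16–57%. Spearman does not move, but that is by construction: ranks do not depend on the median or log-SD. It is not evidence of robustness.

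**Step 4: durations altered by procedures.** Suppose half of the patients who would exceed 7 days have the tube out at days 3–5 because of an early procedure. Spearman power in the Step 2 setting then falls from 77% to about 64%. The 77% therefore depends on the assumption that no durations are altered.

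**Step 5: air leak, once listed.** At 80% power the detectable difference is (1.96 + 0.84)·√(1/n₁ + 1/n₂) SD. If 20% of 125 have an air leak (25 v 100), it is 2.80 × 0.2236 = 0.63 SD. If 30% do (38 v 87), it is about 0.55 SD. Both shares are assumed. If 6 of the 25 were counted as not having an air leak because they were treated or discharged before day 5, power at 0.63 SD would fall from 80% to about 66%.

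**The case against.** The best defence is that section 3 supplies a natural 5-day threshold and says the tube is kept in and further procedures follow in those patients. Tube duration, pleurodesis, IBV and VATS would then all carry air-leak information, and a 5-day split of duration might be what was meant. In part this stands: air leak is captured indirectly, by duration as well as by the three procedures. But section 3 defines air leak by healing of the pleural defect, not by days with a tube, and neither 7b nor 7c refers to it. Air leak may also be recorded under the open list in 4a, but recording it would not create a planned test.

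It can also be said that the study is mainly descriptive and sized on incidence. That is true of the primary objective. The secondary objective sets out to demonstrate a relationship, and 7c promises significance tests for it.

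A reader might infer more: that 7c pools SP and TP, and that an unstratified test would therefore give false positives. The documents do not support this. Section 7c does not say which patients enter the secondary tests; the 100 and 25 appear only as a sample size. Nor is adjustment a demonstrated correction. Assume TP patients have Ppl 2 SD higher and log-duration 0.5 SD longer, with no association within either group. A pooled Spearman is then significant in about 24% of runs and an adjusted one in 5%. But the whole-cohort correlation really is non-zero: (0.8 × 0.2 × 2 × 0.5)/√(1.64 × 1.04) = 0.12. With the same shifts and a within-group correlation of 0.25, pooled power is about 93% and adjusted about 75%. The objective sets no within-group condition, so these are answers to two different questions.

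**Conclusion.** The concern holds as a specification gap in the secondary analysis and should be fixed. Two findings rest on the text alone: 7c gives duration a test that needs an unstated split, and it gives persistent air leak no direct test. They do not make the whole secondary analysis unworkable: the pleurodesis, IBV and VATS comparisons stand, and the primary description of Ppl is untouched.

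The power figures (about 77% for Spearman, 60% and 41% for the two splits) show only that the choice of cut-off matters. They rest on an assumed correlation, an assumed duration distribution and no durations altered by procedures. No power loss can be attributed to the plan itself, since it names no cut-off.

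**What to change.** - **Air leak.** Add persistent air leak (yes/no, by the protocol's own 5-day definition) to 4a and 7b. State when the 5 days start and how patients with an earlier procedure or discharge are classified for analysis. Compare Ppl by that status with the planned t-test.
- **Duration.** Replace the t-test with a pre-specified Spearman correlation between initial Ppl and duration in patients who have a tube. Name one of the three 7a variables as the main Ppl measure. State in advance how durations altered by pleurodesis, IBV or VATS are handled, for example by a sensitivity analysis that ranks them as longest. Any yes/no split for prolonged drainage should have its cut-off fixed before the data are seen and be supportive only.
- **Who is analysed.** State which participants contribute a duration, since sections 5 and 8a also admit needle aspiration while 4a describes a catheter left in place. Say whether SP and TP are combined in the secondary tests. Report the whole-cohort result, with an SP/TP-stratified result as a sensitivity analysis.

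The cost is a few sentences in 4a, 7b and 7c, one field taken from the chart, and slightly more analysis. No extra patients or procedures are needed.

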Routine use of pleural manometry in the evaluation and management of pneumothorax has not yet been adopted, likely due to the historical difficulty in obtaining measurements and the uncertain clinical benefit they provided. Harrejón et al. found that Ppl in spontaneous pneumothorax was greater in patients that required prolonged drainage.¹⁰ These results were later supported by Kaneda et al who also demonstrated the practicality of measuring Ppl in pneumothorax. Their measurements required only up to 30 seconds by using an electronic manometer connected to an intrapleural catheter.¹¹ Still to date, Ppl in TP have yet to be reported.

4. Study Procedures

- a. Patients admitted with spontaneous, iatrogenic, or tension pneumothorax referred to the section of Interventional Pulmonology will be recruited. Using standard sterile technique, a 14fr catheter will be inserted into the pleural space. An electronic manometer (Compass, Medline Industries, Inc.) will be connected in-line to the introducer needle and Ppl will be recorded for 3-5 respiratory cycles. The catheter will then remain in place per routine standards of practice. Outcome data of patients will be collected including indication for chest tube placement, duration of chest tube placement, need for pleurodesis, IBV, and referral for VATS. Patient data will be de-identified and stored on the SAFE (or equivalently password-protected/secure) desktop at each local institution
- b. Johns Hopkins' Interventional Pulmonology (IP) research team will act as the lead coordinating site and [name] will act as the overall study Principal Investigator. This group already has the contact information for planned non-JHU sites (names & emails/phone numbers for PI & study coordinators at each site). The IP research team will be responsible for ensuring each participating institution has IRB approval and up-to-date human subjects' compliance training.. The JHU IP research team will track IRB approval dates and store copies of each non-Hopkins affiliated site's documents (e.g. IRB approval letters, protocols, consent form templates) on a JHU-password-protected shared drive. Dates and protocol versions of materials sent to each site will also be recorded on a spreadsheet to ensure all sites are using the most current materials. If any local IRB requested edits (besides changing PI & institution

Date: 06/14/2021

Principal Investigator: [name]

Application Number: IRB00256185

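### The plan asks which patients will need escalation but defines no any-escalation outcome and no comparator; testing each procedure yes against no would mix patients escalated another way into the comparator and leave few cases per test

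*Combined protocol and SAP*

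**What the plan says.** Section 3 (Background) defines the failure: "If the visceral pleural defect is not healed after 5 days, it is deemed a persistent air leak". It then says that "the chest tube is maintained and more aggressive measures such as pleurodesis, placement of an IBV, or VATS are performed", and adds that no method exists to predict who will come to need these procedures.

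The secondary objective in Section 2 begins: "Demonstrate a relationship between initial intrapleural pressure and presence of persistent air leaks, need for prolonged chest tube drainages, pleurodesis, intrabronchial valve (IBV) placement, and/or" and ends with VATS.

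Section 7b gives the secondary outcome variables as "Duration of chest tube placement, referral for pleurodesis, IBV placement, and/or referral for VATS". Persistent air leak, named in the objective, is not among them.

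The analysis is one sentence in Section 7c: "A student's t-test will be used to determine statistical significance in differences of Ppl in the secondary outcomes listed above". It does not say which two groups each test compares, whether the three procedures are tested separately or together, or how to class a patient who had a different procedure or more than one.

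Section 4a records "duration of chest tube placement, need for pleurodesis, IBV, and referral for VATS", so the parts of a combined outcome are already collected.

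**The concern.** The Background's question is about any escalation against none. The analysis sentence points to the listed outcomes one at a time. A two-sample t-test needs two groups, and for an outcome such as IBV placement these are ordinarily patients who had it and patients who did not. A patient whose air leak was treated only by VATS would then be a no for IBV and a no for pleurodesis.

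Two things follow. Failures in the comparator pull its mean Ppl toward that of the cases, so the expected difference shrinks toward zero. Separately, each test counts only part of the failures as cases, so it is imprecise even with a clean comparator. This is the study's only prognostic analysis. A null result produced this way could be taken to mean that initial Ppl has no predictive value.

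**Working it through.** **The plan's own figure.** Section 7c says "A sample size of 100 SP and 25 TP will be used based on expected incidence of disease in recruitment period", a total of 100 + 25 = 125. No alpha, power, effect size or SD is given, so the figure cannot be reproduced from a power calculation. For orientation, 100 v 25 at two-sided 0.05 detects (1.960 + 0.842) × √(1/100 + 1/25) = 2.802 × 0.2236 = 0.63 SD with 80% power, and 3.242 × 0.2236 = 0.72 SD with 90%. That concerns SP against TP. It says nothing about the procedure outcomes.

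**Assumptions.** The documents give no escalation rate, split between procedures or Ppl SD. The base case assumes F = 25 of N = 125 escalated, k = 8 with a given procedure (about a third), no patient with more than one procedure, a true difference of 0.8 SD between escalated and non-escalated patients that is the same for every procedure, and an equal-variance t-test at two-sided 0.05. The 25 v 100 split that results is not the TP/SP split.

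**Step 1, make-up of the comparator.** Share of failures among the no patients = (F − k)/(N − k) = 17/117 = 14.5%. Expected difference = 0.8 × (1 − 0.145) = 0.68 SD.

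**Step 2, precision (SD units).**
- One procedure v everyone else (8 v 117): √(1/8 + 1/117) = 0.365
- One procedure v no escalation (8 v 100): √(1/8 + 1/100) = 0.367
- Any escalation v none (25 v 100): √(1/25 + 1/100) = 0.224

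The ratio 0.365/0.224 is 1.63. Cleaning the comparator leaves the standard error almost unchanged, so the loss of precision comes from having 8 cases and not 25.

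**Step 3, power.** The mixed comparison was simulated (at least 20,000 t-tests). The two clean ones follow from the noncentral t, with noncentrality 0.8/0.367 = 2.18 on 106 df and 0.8/0.2236 = 3.58 on 123 df.
- 8 v 117 mixed: 42.9%
- 8 v 100: 57.8%
- 25 v 100: 94.4%

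The mixed comparator costs 57.8 − 42.9 = 14.9 points. The small case group costs 94.4 − 57.8 = 36.6 points.

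**Step 4, other assumptions (N = 125, 0.8 SD).**

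| Escalated | With the procedure | Failures in comparator | Procedure v everyone else | Procedure v no escalation | Any v none |
|---|---|---|---|---|---|
| 12 | 4, no overlap | 8/121 = 6.6% | 29% | 34% | 74% |
| 25 | 8, no overlap | 17/117 = 14.5% | 43% | 58% | 94% |
| 38 | 13, no overlap | 25/112 = 22.3% | 51–52% | 76% | 98% |
| 25 | 17, about two procedures each (25 × 2/3) | 8/108 = 7.4% | 79% | 85–86% | 94% |

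If every escalated patient had all three procedures, no failures would be left in the comparator and each single test would equal the combined one.

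**The case against.** The strongest reply is that the plan never says each procedure is tested against all other patients. Section 7c defines no groups, and the and/or in Sections 2 and 7b leaves a combined outcome possible. This stands: the yes/no reading is an inference. It does not remove the point. No combined outcome is specified either, and in a study that Section 4g describes as nonblinded, the choice would otherwise be made after the data are seen.

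A reader might go further and infer that every comparator group is bound to contain patients who failed and were rescued another way. The documents do not support that. It requires some patients to be escalated by one route only. Section 3 introduces the procedures with such as and joins them with or, without calling them mutually exclusive or interchangeable, and the and/or elsewhere allows several in one patient.

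A reader might also credit the whole gap between 43% and 94% to the mixed comparator. The working shows that it accounts for less than a third of the gap (14.9 of 51.5 points).

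Finally, pooling can itself cost something. Nothing in the documents says that the choice of procedure is unrelated to Ppl. If Ppl differs by procedure, a combined outcome could blur that difference, and the calculated advantage assumes the same shift for all three. This stands as a reason to keep the breakdown by procedure. These are also secondary outcomes in a study whose primary aim is descriptive, and the raw data would still allow a combined analysis later, though not a prespecified one.

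**Conclusion.** The point holds in conditional form. The plan presents three procedures as escalations for one failure, asks who will need them, and then defines neither a combined outcome nor comparison groups. If each procedure is tested yes against no, and some patients are escalated only by another route, the Ppl difference is diluted toward zero and each test has few cases.

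Without overlap, and with 12 to 38 of 125 patients escalated, the failures in the comparator run from 6.6% to 22.3%. Power is 29% to 52% for a single procedure against 74% to 98% for any escalation. With about two procedures per patient and 25 escalated, the gap narrows to 79% against 94%. All of these rest on the assumed rates, split and 0.8 SD; none can be taken from the documents. The direction is firmer than the size: in every scenario tabulated the combined comparison did better. The matter should be fixed, but it concerns secondary outcomes and does not touch the primary objective.

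**What to change.** In Section 7b, add one combined secondary outcome: any escalation, meaning pleurodesis, IBV placement or VATS. State whether a referral or a completed procedure counts, since Section 4a records need for pleurodesis while Section 7b lists referral for it.

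In Section 7c, compare Ppl between patients with any escalation and patients with none. Report Ppl for each procedure descriptively, including how many patients had more than one. If a single procedure is tested, use patients with no escalation of any kind as the comparator.

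The cost is a few sentences, with no new data and no change to patient care. The downside is small: the combined outcome does not show which procedure drives a difference and could blur one if Ppl varies by procedure. The descriptive breakdown covers this.

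### Section 7c plans only t-tests of mean Ppl for the secondary outcomes, so it gives no risk estimate, interval or measure of discrimination for the prediction gap that motivates the study

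*Combined protocol and SAP*

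**What the plan says.** The secondary objective in section 2 is worded as association: "Demonstrate a relationship between initial intrapleural pressure and presence of persistent air leaks", followed by prolonged drainage, pleurodesis, IBV and VATS. Section 7b lists the secondary outcome variables as "Duration of chest tube placement, referral for pleurodesis, IBV placement, and/or referral for VATS", that is, one duration and three yes/no events.

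Section 7c then says that a Student's "t-test will be used to determine statistical significance in differences of Ppl in the secondary outcomes listed above". No other analysis is named for these outcomes. The documents contain no regression, odds ratio, AUC, sensitivity, specificity, prognostic cut-off or confidence interval.

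The reason given for studying these outcomes is prognostic. Section 3 states that "there is currently no method to predict which patients will require these more invasive procedures" and draws the contrast with effusions: "The lack of prognostic indicators is not the case in pleural effusions, however". Section 9 adds that the findings may inform later management.

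**The concern.** The background asks a forward question: given a patient's initial pressure, how likely is an invasive procedure? Section 7c asks the reverse: given that a patient did or did not have the procedure, did mean pressure differ? The two share a null hypothesis, but a p-value for the second does not say how large the answer to the first is.

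A difference in means can be statistically clear while the two pressure distributions largely overlap. If significance is all that is reported, the trial cannot say whether initial Ppl comes close to filling the gap that section 3 names. A reader may then take a small p-value as evidence of a prognostic indicator.

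**Working it through.** **Inputs**
- Patients: 100 SP + 25 TP = 125 (section 7c).
- Alpha and sidedness: not stated; two-sided 5% assumed.
- Number with a given outcome: not stated; 12, 25 and 40 of 125 assumed (about 10%, 20% and 32%).
- Distribution and SD of Ppl: not stated; normal with equal SDs assumed, so differences d are in SD units.

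There is no figure of the plan's own to reproduce. Section 7c says "A sample size of 100 SP and 25 TP will be used based on expected incidence of disease in recruitment period", with no power, effect size or SD.

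**Step 1. Smallest observed difference that is significant.** d* = t(0.975, 123) × √(1/n1 + 1/n0), with t = 1.979.
- 12 v 113: 1.979 × 0.3036 = 0.60
- 25 v 100: 1.979 × 0.2236 = 0.44
- 40 v 85: 1.979 × 0.1917 = 0.38

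**Step 2. Discrimination at that difference.** AUC = Φ(d*/√2), with an approximate 95% CI by Hanley-McNeil.

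| Split | d* | AUC at p = 0.05 | 95% CI |
|---|---|---|---|
| 12 v 113 | 0.60 | 0.66 | 0.49 to 0.84 |
| 25 v 100 | 0.44 | 0.62 | 0.49 to 0.75 |
| 40 v 85 | 0.38 | 0.61 | 0.50 to 0.71 |

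If the outcome occurred in half the patients (62 v 63), d* would be 0.35 and the AUC 0.60. Using the 100 SP patients alone, with 10% to 50% having the outcome, the boundary AUC is 0.61 to 0.68.

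**Step 3. What the middle case means for patients (25 v 100).** At 80% specificity, sensitivity = 1 − Φ(0.842 − 0.443) = 0.34. PPV = (0.34 × 0.20) / (0.34 × 0.20 + 0.20 × 0.80) = 0.30, against a base rate of 0.20. About two thirds of the patients who go on to the procedure would be missed. The 80% specificity is for illustration only.

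**Step 4. True effects the t-test detects with 80% power.** d = (1.960 + 0.842) × √(1/n1 + 1/n0) = 0.85, 0.63 and 0.54 for the three splits. The corresponding AUCs are 0.73, 0.67 and 0.65.

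**Step 5. The opposite error: would a good predictor be missed?** A true AUC A corresponds to d = √2 × z(A): 0.74 for 0.70, 0.95 for 0.75 and 1.19 for 0.80. Power of the t-test, from the noncentral t with 123 df:

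| True AUC | 12 v 113 | 25 v 100 | 40 v 85 |
|---|---|---|---|
| 0.70 | 68% | 91% | 97% |
| 0.75 | 88% | 99% | over 99% |
| 0.80 | 97% | over 99% | over 99% |

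**Step 6. Precision if the AUC is reported.** At a true AUC of 0.80, the Hanley-McNeil 95% half-width is about 0.15, 0.11 and 0.09 for 12, 25 and 40 events.

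**The case against.** The best defence is that the plan does what its objective says. The objective promises a relationship, and comparing Ppl between patients with and without a yes/no outcome tests for one. No objective, outcome definition or analysis statement promises a prediction tool; the prognostic language is in the background. Sorting by outcome is not an error in itself. Under equal-variance normality the t-test and a one-predictor logistic model address the same null, and the group means and SDs yield the AUC by the formula in step 2. All of this stands. It means that 7c is not invalid for the objective as worded; what is missing is a commitment to estimate and report.

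A reader might also infer four stronger things that the documents do not support:
- **That any significant result would mean near-chance discrimination.** The AUCs in step 2 describe a result exactly at p = 0.05. Larger observed differences imply better discrimination.
- **That p > 0.05 would throw away a useful predictor.** Step 5 shows at least 97% power at an AUC of 0.80. The risk is material only for a modest predictor with few events (68% power at an AUC of 0.70 with 12 events).
- **That the analysis only repeats earlier work.** Section 3 says that an earlier study "found that Ppl in spontaneous pneumothorax was greater in patients that required prolonged drainage", with later support. That concerns drainage time in spontaneous pneumothorax. The documents report no earlier comparison of Ppl for pleurodesis, IBV or VATS, and this study also recruits iatrogenic and tension cases.
- **That atmospheric pressure (0 cmH2O) is a ready-made prognostic cut-off.** The abstract uses it in a definition of tension, which it calls controversial. Nothing ties it to later procedures.

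**Conclusion.** The point holds as a gap between motivation and analysis. Section 7c tests association and stops there, while section 3 says that the open question is who will need invasive procedures. Under the assumptions listed, the p = 0.05 boundary lies at an AUC of about 0.61 to 0.66 for 12 to 40 events among 125 patients. A significant t-test by itself therefore says little about predictive ability.

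The structural part, that no estimate, interval or discrimination measure is planned, rests on the text alone. The size rests on an assumed alpha, outcome numbers, normality and equal SDs, none of which the documents give. It applies to the yes/no outcomes. Chest tube duration is continuous, and 7c gives no cut-point to form two groups, so it needs its own method.

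**What to change.** In section 7c, for each yes/no secondary outcome:
- Keep the t-test if wanted, and add a logistic regression of the outcome on initial Ppl as a continuous predictor.
- Name in advance which of the three measures in 7a (inspiratory, expiratory or mean Ppl) is the predictor.
- Report the odds ratio per stated pressure unit and the AUC, each with a 95% CI.
- State that any claim that Ppl predicts these outcomes rests on the AUC and its interval, not on the t-test p-value.
- Label sensitivity or specificity at any cut-off as exploratory.

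This uses data that section 4a already collects, so it needs no extra patients or measurements, only SAP wording and a few lines of analysis. The downside is that with few events the intervals will be wide (step 6), which shows how much the data can say. The wording should be fixed before the outcome data are analysed.
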